8. OPTIONAL MECHANISTIC SUBSTUDIES

Subjects in ARC007 are eligible to participate in the optional collection of saliva and peripheral blood specimens for future studies designed to better understand the biological basis and treatment of food allergy. The provision of these additional specimens is voluntary and does not affect the subject's participation in ARC007. The parents/guardian and subject, as appropriate, will be asked to sign separate informed consent and assent forms to participate in this sub-study. The additional tubes of peripheral blood are to be collected at the same time points as the routine laboratory work in ARC007 and do not require additional visits or phlebotomy. The saliva specimens will be collected as part of an ongoing collaboration with researchers at Cincinnati Children's Hospital Medical Center to analyze the salivary mRNA transcriptome of participants receiving OIT, as outlined further in [Appendix 7](#).

9. STATISTICAL CONSIDERATIONS

This protocol outlines the major statistical considerations for the ARC007 study. Full details on the statistical methodology to be used in the analysis and data handling for this trial will be described in the statistical analysis plan (SAP) to be developed prior to database lock and statistical analysis.

Data will be summarized using descriptive statistics within treatment group. No specific hypothesis testing or comparisons between the treatment groups are planned for this study.

Details of within-group comparisons relative to baseline values and any exploratory comparisons between groups will be described in the SAP.

Descriptive statistics will be presented in the following manner:

- Continuous data (ie, age, body weight, and height) will be summarized descriptively by mean, standard deviation, median, and range.
- Categorical data (ie, sex and race) will be presented as enumerations and percentages.

Data will be summarized by treatment group and treatment phase.

Data will be summarized in tables for each treatment group, treatment groups combined, and treatment phase.

Data will be listed for each subject.

The end of study is defined as the date of the last visit of the last subject.

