Statistical Considerations	
ARC007 is a safety study that will add critical placebo-controlled observations to the ongoing safety database of AR101. As such, there are no efficacy endpoints in the study, no specific efficacy-related hypotheses to be tested, and thus no prospective sample size calculations performed related to the clinical effectiveness of AR101 treatment versus placebo.
 
A sample size of up to 500 subjects, randomized in a 2:1 ratio to AR101 or placebo, along with subjects enrolled in other studies in the clinical program will provide a sufficient number of subjects to fulfill the regulatory requirement for data on at least 600 subjects dosed for 6 months at 300 mg/d.
 
Data will be summarized using descriptive statistics and will be displayed by treatment group. No specific hypothesis testing or comparisons between the treatment groups is planned for this study. Further details on the analytical approach and any exploratory comparisons between treatments will be provided in the statistical analysis plan. See Section 9 of the protocol for further information.

Table of Contents

1. BACKGROUND AND RATIONALE.....	19
1.1 Background.....	19
1.2 Clinical Trials of AR101.....	20
1.2.1 ARC001 Trial.....	20
1.2.2 ARC002 Trial.....	21
1.2.3 ARC003 Trial.....	21
1.3 Rationale for the Current Study	22
1.4 Known and Potential Risks and Benefits of AR101.....	23
1.4.1 Risks.....	23
1.4.2 Benefits	23
2. OBJECTIVES	24
2.1 Primary Objective	24
2.2 Secondary Objectives.....	24
3. STUDY DESIGN.....	24
3.1 Study Periods	25
3.2 Initial Escalation	26
3.3 Up-Dosing.....	26
3.4 Treatment Unblinding and Rollover to Studies ARC011 and ARC008	27
4. SELECTION AND WITHDRAWAL OF SUBJECTS	28
4.1 Inclusion Criteria	28
4.2 Exclusion Criteria	28
4.3 Early Termination	30
4.3.1 Criteria for Early Termination	30
4.3.2 Follow-up of Subjects Who Discontinue Treatment	31
4.3.3 Subject Replacement.....	31
5. STUDY TREATMENT	31
5.1 Formulation, Packaging, and Labeling	31
5.2 Preparation, Administration, and Dosage	32
5.3 Drug Accountability.....	33
5.4 Assessment of Compliance with Study Treatment and Monitoring	33
5.5 Modification of Study Treatment.....	33

5.6	Concomitant Medications	33
5.7	Prophylactic Medications.....	34
5.8	Rescue Medications	34
5.9	Symptomatic Treatment for Chronic and/or Recurrent Adverse Events	34
5.10	Prohibited Medications	34
6.	STUDY PROCEDURES	35
6.1	Enrollment and Randomization	35
6.2	Screening and Baseline	35

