## 7.2 Programming Conventions

Unless stated otherwise, the term “descriptive statistics” refers to the number of subjects (n), mean, median, standard deviation, minimum, and maximum for continuous variables and frequencies and percentages for categorical variables.

Unless specified otherwise, the denominator for percentages for categorical data will be based on the number of subjects or observations with nonmissing data appropriate for summary purposes. The denominator for percentages for incidence data (such as adverse events) will be based on the number of subjects in the analysis population “at risk”.

Minimum and maximum values will be presented at the precision of the original value, means, medians will be rounded to 1 decimal place greater than the precision of the original value, standard deviations and standard errors will be rounded to 2 decimal places greater than the precision of the original value. Percentages will be rounded to 1 decimal place. Percentages that round down to 0 or up to 100% will be displayed as “< 0.1%” and “> 99.9%”, respectively.

All summary tables will be presented by treatment group displayed as AR101 and placebo. For disposition, demographic, and other summaries of baseline and history data, a total column for both treatment groups combined will be included.

All relevant data collected in the database will be included in data listings and sorted by treatment group, subject number, and visit and time point as appropriate. The treatment group will be displayed by AR101 then placebo.

Unscheduled visits will be listed but not included in by-visit summaries. Results from unscheduled visits may be used as baseline values and for other derivations not tied to visit names (for example, unscheduled visits are included in the determination of worst postbaseline values for laboratory shift tables).

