## **9.8 Safety Analyses**

Safety will be assessed by all the endpoints defined in [Section 4](#).

Safety data will be summarized descriptively and the safety population will be used for all summaries of safety parameters, unless otherwise noted. Safety listings will include all randomized subjects sorted by treatment group (AR101 then placebo).

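### The SAP puts AR101 and placebo safety results side by side with no estimated difference and no measure of its uncertainty; for repeat-event rates the summary tables do not allow a reader to supply one

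*Protocol*

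**What the plan says.** Protocol Section 9 is explicit: "No specific hypothesis testing or comparisons between the treatment groups are planned for this study". It then adds: "Details of within-group comparisons relative to baseline values and any exploratory comparisons between groups will be described in the SAP". The synopsis says much the same: "Further details on the analytical approach and any exploratory comparisons between treatments will be provided in the statistical analysis plan".

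The SAP takes the descriptive route. Section 9.8 states: "Safety data will be summarized descriptively and the safety population will be used for all summaries of safety parameters, unless otherwise noted". Section 7.2 limits descriptive statistics for categorical data to "frequencies and percentages for categorical variables", and fixes the layout: "All summary tables will be presented by treatment group displayed as AR101 and placebo".

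Sections 9.8.1 to 9.8.5 cover adverse events, GI events, anaphylaxis, epinephrine use and food allergy episodes in that form, for ages 4-11, 12-17 and 4-17 and mostly by study period. Section 9.8.1 adds exposure-adjusted rates, defined as total events over total subject-years, again by arm. Section 7.2 has a rounding rule for standard errors, but no section asks for a risk difference, rate ratio, confidence interval or test. The SAP does not say whether exploratory between-arm comparisons were considered and left out.

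**The concern.** Protocol 9.4 and SAP Section 5 present the study's contribution as placebo-controlled safety data, and one third of up to 500 children are allocated to placebo. The planned output stops one step short of using that control: it shows two columns and leaves the contrast, and its precision, to the eye.

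At stake is how the primary endpoint and the main secondary harms are read. With roughly 167 placebo subjects, an excess of a few percentage points may or may not be compatible with no effect, and two percentages do not tell the reader which. Even where an interval includes zero, its upper limit says how large an excess remains possible, which is often the more useful statement in a safety report.

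**Working it through.** **Inputs.** Up to 500 subjects, 2:1 (Protocol 9.4): 500 × 2/3 ≈ 333 AR101 and 167 placebo, assuming full enrolment and all dosed. From ARC001 (Protocol 1.2.1): any TEAE 97% v 85%; discontinuation due to an AE 4/29 v 0/26. The protocol also puts EoE at an estimated 3% of OIT recipients (1.4.1). The other rate pairs below are assumptions.

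**The plan's own figure.** The 500 rests on a pooled exposure target of at least 600 subjects across the programme. No alpha, power, effect size or precision is given, so there is no between-arm calculation to reproduce.

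**Step 1: what side-by-side percentages hide.** In ARC001, 4/29 = 13.8% v 0/26 = 0%. The Wilson 95% limits are 5.5% to 30.6% for AR101 and 0% to 12.9% for placebo. Newcombe's interval for the difference d = p1 − p2 is

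- lower = d − √[(p1 − l1)² + (u2 − p2)²] = 13.8 − √(8.3² + 12.9²) = −1.5 points
- upper = d + √[(u1 − p1)² + (p2 − l2)²] = 13.8 + √(16.8² + 0²) = 30.6 points

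Fisher's exact p is 0.11. A split of 14% v 0% looks decisive and, at that size, is not.

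**Step 2: the same formula at 333 v 167.**

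| Events, AR101 v placebo | Source of rates | Difference, points (95% CI) |
|---|---|---|
| 323 v 142 (97% v 85%) | ARC001 | 12.0 (6.7 to 18.3) |
| 47 v 0 (14% v 0%) | ARC001 | 14.1 (10.1 to 18.3) |
| 33 v 5 (10% v 3%) | assumed | 6.9 (2.2 to 11.0) |
| 17 v 3 (5% v 2%) | assumed | 3.3 (−0.5 to 6.5) |
| 10 v 2 (3% v 1%) | assumed | 1.8 (−1.6 to 4.4) |
| 10 v 0 (3% v 0%) | 3% as for EoE; 0% assumed | 3.0 (0.4 to 5.4) |
| 3 v 0 (1% v 0%) | assumed | 0.9 (−1.4 to 2.6) |

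With no placebo events, 8 AR101 events (2.4%) give −0.1 to 4.7 and 9 events (2.7%) give 0.1 to 5.1. Zero events in 167 still allows a true rate up to 1 − 0.025^(1/167) = 2.2% (two-sided 95%).

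**Step 3: what a reader can and cannot rebuild.** Each row above needs only subject counts and denominators, which the SAP tabulates. Event rates are different. Take an assumed arm with 60 events in 20 affected subjects. Approximate the variance of the event total by the sum of squared per-subject counts. With equal follow-up in 333 subjects, this drops a centring term of 60²/333 = 10.8, the same in each case.

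- Three events each: 20 × 3² = 180; SE of the log rate = √180/60 = 0.224; 95% limits are the rate divided and multiplied by exp(1.96 × 0.224) = 1.55.
- Fifteen subjects with one event and five with nine: 15 + 5 × 81 = 420; SE = √420/60 = 0.342; factor 1.95.
- Treating all 60 events as independent (Poisson): SE = √60/60 = 0.129; factor 1.29.

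The event total and the number of subjects affected are the same throughout, yet the interval differs, and the Poisson shortcut is too narrow in both patterns. The SAP tabulates episodes per subject for anaphylaxis, epinephrine use and food allergy episodes, but not events per subject for TEAEs or hypersensitivity events. Those intervals need subject-level data.

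**The case against.** The strongest defence is that the descriptive approach is declared openly in the protocol and the SAP, and that the sample size rests on pooled exposure rather than on a between-arm contrast. No planned result is invalid, and nothing in the two documents conflicts. All of that stands, and it makes this an improvement rather than an error.

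Four stronger readings are tempting, and the documents do not support them:

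- **That the SAP fails to deliver something promised.** The protocol refers to "any exploratory comparisons between treatments will be provided in the statistical analysis plan". The word any makes this conditional, and an SAP with no such comparisons is consistent with it. At most, the SAP leaves the matter unaddressed.
- **That chance and drug effect cannot be told apart.** For anaphylaxis, epinephrine use, SAEs and AE discontinuation, the SAP gives subject counts by arm with at-risk denominators, so anyone can compute an unadjusted interval, as Step 2 does.
- **That age stratification is ignored.** Nearly every safety summary is already given by age group and arm. Only a stratified contrast is missing.
- **That intervals would resolve rare harms.** Near 1% the limit is about 167 placebo subjects, and no added column changes that.

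There is also a fair technical objection to modelling rates without a rule for sparse data. In a trial fit with 10 single-event AR101 subjects and no placebo events, the negative binomial model returned no standard errors and the Poisson standard error was about 17,000. A ratio is not estimable there, and the fix has to say what happens instead.

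**Conclusion.** The point holds as a cheap improvement. The planned outputs give no estimate of the AR101-placebo difference and no measure of its uncertainty, although the study is presented as a source of placebo-controlled safety data.

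For binary harms the gain is convenience and one prespecified method in place of intervals chosen by each reader. It matters most for harms of roughly 3% to 10%, where the interval may fall either side of zero. For exposure-adjusted rates the gain is real information: without subject-level data, no valid interval can be formed for overall TEAE rates or for the hypersensitivity secondary endpoint.

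The sizes rest on 500 subjects all dosed, a 333/167 split, and illustrative rates apart from those taken from ARC001 and the EoE estimate. ARC001 was a 55-subject trial in ages 4 to 26 with food challenges, so its rates may not carry over. The 60-event example is assumed and shows only the mechanism.

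**What to change.** In SAP 9.8, for the overall study period and ages 4-17 only:

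1. **Binary endpoints.** Add the AR101 minus placebo risk difference with 95% CI for any TEAE, SAEs, discontinuation due to AEs, discontinuation due to chronic/recurrent GI AEs, anaphylaxis, epinephrine use and accidental food allergen exposure. Stratify by randomised age group (4-11, 12-17) where counts allow; otherwise use an unstratified Newcombe score or exact interval. Name the stratum weights and the count below which the unstratified interval applies.
2. **Event rates.** For exposure-adjusted rates of TEAEs and hypersensitivity AEs, add a rate ratio with 95% CI whose variance allows for repeat events (negative binomial or robust variance, log-exposure offset, age group as covariate). If either arm has too few events to fit the model, report the per-arm rates only.
3. **Status.** Label all intervals descriptive, with no p-values and no multiplicity claims.

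Failing that, one sentence should say that exploratory between-arm comparisons were considered and omitted, and why.

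The cost is SAP wording, a few table columns and some programming; no new data are needed. The downside is several unadjusted intervals, which readers may over-interpret. Restricting them to one period and one age range keeps the number small.

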9.1 Analysis Populations

The primary population of analysis for all analyses will be the safety population. The Safety population will consist of all subjects who receive study treatment during ARC007.

A per-protocol population, limited to subjects who have no major protocol deviations and who undergo Exit Visit procedures, may be defined. Exclusions will be determined by data review and documented before database lock.

Additional analysis populations may be defined in the SAP.

9.2 Study Endpoints

9.2.1 Primary Endpoint

The primary endpoint is the frequency of TEAEs, including SAEs, during the overall study period.

9.2.2 Secondary Endpoints

- Frequency of premature discontinuation of dosing due to AEs
- Frequency of premature discontinuation of dosing due to chronic/recurrent GI AEs
- Proportion of chronic/recurrent GI AEs resolving at 2, 4, and \geq 12 weeks following cessation of dosing
- Frequency of allergic reaction (hypersensitivity) AEs occurring during up-dosing, normalized for duration of treatment
- Frequency of anaphylaxis as defined in the protocol
- Frequency of use of epinephrine as a rescue medication
- Frequency of accidental ingestion of peanut and other allergenic foods and severity of any resultant reactions

- Assessment of asthma control using the ACT questionnaire and frequency of use of asthma rescue medication (short acting beta-agonists) in subjects with asthma

9.2.3 Exploratory Endpoints

- Changes in peanut-specific and peanut component-specific serum IgE and IgG4 levels
- Changes in peanut SPT mean wheal diameter
- Changes in Total Nasal Symptom Score in subjects with allergic rhinitis
- Changes in scores of FAQLQ and the FAIM questionnaire

9.3 Subject and Demographic Data

9.3.1 Baseline Characteristics and Demographics

Summary descriptive statistics for baseline and demographic data will be provided for all enrolled subjects. Baseline characteristics (body weight and height) and demographic data (age, race, and sex) will be collected.

Statistical presentation for baseline and demographic characteristics may be further summarized by baseline peanut-specific serum IgE.

9.3.2 Use of Medications

All medications used will be coded using the WHO Drug Dictionary. The number and percentage of subjects receiving concomitant medications or therapies will be summarized descriptively.

9.3.3 Study Disposition

The number and percent of subjects in each analysis population will be summarized. The number of subjects who complete the study, discontinue prematurely, and their reason for study discontinuation will be tabulated. Total duration on treatment and total duration on study will also be summarized.

9.3.4 Adverse Events

Adverse events will be coded on the basis of the Medical Dictionary for Regulatory Authorities terminology. Events will be tabulated by system organ classification and preferred term. Selected summaries will also be prepared by severity and relationship to study treatment.

9.4 Sample Size and Power Calculations

ARC007 is a safety study that will add critical placebo-controlled observations to the ongoing safety database of AR101. As such, there are no efficacy endpoints in the study, no specific efficacy-related hypotheses to be tested, and no prospective sample size calculations performed related to the power to detect a pre-specified treatment effect size.

A sample size of up to 500 subjects, randomized in a 2:1 ratio to AR101 or placebo, along with subjects enrolled in other studies in the clinical program will provide a sufficient number of subjects to fulfill the regulatory requirement for data on at least 600 subjects dosed for 6 months at 300 mg/d.

9.5 Web-Based Data Collection and Management System

Data collection will occur via an EDC system to allow easy access to enrollment 24 hours/day, 7 days/week. Upon enrollment, a form submission schedule is generated for each subject by study visit that permits direct access to each electronic CRF for data entry. As data are entered, they are validated through range and within-form consistency checks. The Investigator will be required to ensure that all CRFs are completed in a timely fashion for all subjects at their site.

9.6 Certification in the Use of Electronic Data Entry System

The clinic and laboratory staff will be trained in the use of the EDC system. Once certified, users are permitted to enter data into the production system. Access is password controlled. Certification for use of the EDC system will be completed via telephone and/or web-cast training.

9.7 Data Management

Information regarding the subject's history, laboratory tests, evaluation of allergic response, and follow-up status will be stored and processed through the data center. Quality control procedures and a feedback system between the data center and the sites will be instituted to ensure the accuracy and completeness of the data collected.

9.8 Access to Data

The investigational sites shall periodically permit authorized representatives of the IND/study Sponsor, and/or regulatory health authorities to examine clinical records and other source documents for the purpose of safety monitoring, quality assurance reviews, inspections, audits, and evaluations of the study progress throughout the entire study period. The Investigator is required by law and applicable guideline (21 CFR 312.62 and ICH E6) to keep accurate case records for at least 2 years after the last approval of a marketing application in an ICH region and until there are no pending or contemplated marketing application in an ICH region. These documents should be retained for a longer period however if required by the applicable local regulatory requirements or by an agreement with the Sponsor.

10. QUALITY CONTROL AND QUALITY ASSURANCE

10.1 Statement of Compliance

This study will be conducted using current Good Clinical Practice (GCP), as delineated in the 21 CFR Parts 50, 54, 56, and 312 and in the ICH E6, and according to the criteria specified in this study protocol. Before study initiation, the protocol and the informed consent documents (informed consent form and assent forms) will be reviewed and approved by an appropriate IRB(s)/EC(s) as well as FDA and other applicable regulatory health authority(ies). Any amendments to the protocol will also be approved by the Sponsor, IRBs/ECs, and submitted to the applicable health authorities before they are implemented. Any amendments to the consent materials must also be approved by the Sponsor and IRB(s)/EC(s) before they are implemented.

10.2 Informed Consent and Assent

The informed consent form (ICF) is a means of providing information about the study to the parent/guardian of a prospective subject and allows for an informed decision about participation in the study. Because the study population will be comprised of children, parents or legal guardians will be asked to read, sign, and date an ICF before a child enters the study, takes IP, or undergoes any study-specific procedures. Children will sign an assent form, as required by the IRB/EC. Consent materials for parents/guardians who do not speak or read English will be translated into the appropriate language. The ICF and assent form will be reviewed to determine whether a revision is required whenever the protocol is amended, or new safety information becomes available. A copy of the ICF will be given to a prospective parent/guardian for review. The Investigator or designee, in the presence of a witness, will review the ICF and answer questions, as well as emphasize the need to avoid allergen exposure other than to IP, and the importance and necessity to continue exposure to IP to induce desensitization. The prospective subject (as age appropriate) and subject's parent/guardian will be told that being in the study is voluntary and that he or she may withdraw, or withdraw his/her child, from the study at any time, for any reason.

